## **4. DESCRIPTION OF THE STUDY**

The design of the study is:

- Observational
- Retrospective
- Non-comparative
- Not blinded
- Monocentric
- National

This methodologic choice is linked to the search of current practice data, and to the small number of surgeons who have so far use SYMBOL CUP DMR HA or SYMBOL CUP DM CEM, on large consecutive series of patients, thus enabling sufficient consecutive patient recruitment, and who, moreover, maintain a standard medical file record at 2-year follow-up with all the classic endpoints.

### **4.1. DESCRIPTION OF MEASURES TAKEN TO REDUCE AND AVOID BIAS**

Consecutive recruitment with provision of sampling frame data.

## **5. STUDY FEASABILITY**

The clinical research associate (CRA) delegated by the sponsor will make two or three visits to the investigational center:

- An inclusion visit to confirm the investigator's adherence to the protocol and to define the procedures for extracting and transferring anonymized data from the electronic patient record management system. As this is a single-center study, this visit will take place before the protocol is submitted to the CNIL.
- A visit to extract and transfer anonymized data from patient files, and to call patients to obtain their two-year follow-up data. On this occasion, patients will be informed that they may object to the inclusion of their information in this study. During this visit, the sponsor's clinical research associate will check that the data are consistent with the contents of the patient files. He/she will confirm the completeness of the cohort, with consecutive placement of dual-mobility acetabular implants. An anonymized list of all THA during the recruitment period will be obtained and checked to establish the sampling frame. This visit will take place at the start of the study.
- An additional visit by the CRA, to obtain missing data and resolve discrepancies, will take place if necessary.

## **6. RÉALISATION PRATIQUE DU PROTOCOLE.**

### **6.1. DÉROULEMENT DES VISITES LIÉES A L'ÉTUDE**

The clinical research associate (CRA) delegated by the sponsor will make two or three visits to the investigational center:

- An inclusion visit to confirm the investigator's adherence to the protocol and to define the procedures for extracting and transferring anonymized data from the electronic patient record management system. As this is a single-center study, this visit will take place before the protocol is submitted to the CNIL.
- A visit to extract and transfer anonymized data from patient files, and to call patients to obtain their two-year follow-up data. On this occasion, patients will be informed that they may object to the inclusion of their information in this study. During this visit, the sponsor's clinical research associate will check that the data are consistent with the contents of the patient files. He/she will confirm the completeness of the cohort, with consecutive placement of dual-mobility acetabular implants. An anonymized list of all THA during the recruitment period will be obtained and checked to establish the sampling frame. This visit will take place at the start of the study.

- An additional visit by the CRA, to obtain missing data and resolve discrepancies, will take place if necessary.

In the event of death reported by the patient's entourage without a date, the surgeon will question the civil registry of the patient's commune of birth to obtain the date and cause of death.

## **6.2. SUMMARY OF PATIENT FOLLOW-UP**

Patient follow-up is the surgeon's current practice. The protocol does not require any follow-up modalities additional to usual practice. In the event of missing data, the surgeon or secretariat will repeat a telephone call to the patients concerned, as usual, to ask follow-up questions. In the event of death reported by the patient's entourage without a date or explanation, the surgeon will question the civil registry of the patient's commune of birth.

## **6.3. DESCRIPTION OF THE GENERAL LOGISTICAL ORGANIZATION OF THE STUDY**

The registered protocol and the copy of the database will be produced in 3 copies:

- The first to the investigator
- The second to the sponsor
- The third to the statistician.

All exchanges will be made by written mail transfer and USB key with acknowledgement of receipt. Any question raised by the statistician will be forwarded to the sponsor, who will obtain the investigator answer.

## **6.4. BIOLOGICAL SAMPLES AND ANALYSES**

Not applicable

# **7. ELIGIBILITY CRITERIA**

## **7.1. INCLUSION CRITERIA**

Any patient operated by [name] who has undergone hip replacement surgery with SYMBOL CUP DMR HA or SYMBOL CUP CEM acetabular implant and having reach 2-year follow-up on March 01, 2018.

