## 1. SUMMARY OF THE STUDY

TITLE	Retrospective Observational Cohort Study SYMBOL CUP 2
SHORT TITLE	SYMCOR-2
INVESTIGATOR	[name] [name]
SPONSOR	DEDIENNE SANTE S.A.S.
JUSTIFICATION / CONTEXT	Documentation of the clinical efficacy and safety of SYMBOL CUP DMR HA and SYMBOL CUP DM CEM dual mobility acetabular implants.
METHODOLOGY	Retrospective observational cohort study
MAIN OBJECTIVE	Estimate the safety of these implants under normal conditions of use
PRIMARY ENDPOINT	Implant survival rate at 2-year follow-up
SECONDARY OBJECTIVE	Estimate the efficacy of these implants under normal conditions of use
SECONDARY ENDPOINTS	
 
- Safety: Intra and extra-prosthetic dislocation rates
 
- Safety: Incidence of other adverse events
 
- Effectiveness: Harris Hip Score (HHS)
 
- Effectiveness: Devane classification
 
- Effectiveness: Charnley classification
 

INCLUSION CRITERIA	
 
- Any patient operated by [name] who has undergone hip replacement surgery with SYMBOL CUP DMR HA or SYMBOL CUP CEM acetabular implant.
 
- Patient having reach 2-year follow-up on March 01, 2018
 

NON-INCLUSION CRITERIA	
 
- Explicit refusal by the patient to allow data describing his pathology and treatment to be included in this study.
 
- Minor patients or patients under guardianship.
 

RESEARCH PROCESS	
Retrospective collection of clinical data:
 
 
- Recorded in the orthopedic surgery department's patient files, from the patient's pre-surgical assessment to the latest news at 2-year follow-up.
 
- Obtained by telephone interview for data up to 2-year follow-up, if the medical file does not provide all the source information. The telephone interview will be carried out by the investigator (or his secretariat) or by a clinical research associate delegated by the sponsor and approved by the investigator.
 

NUMBER OF SUBJECTS	Minimum total number of subjects: n=20
PLANNED NUMBER OF CENTERS	Single-center, single-investigator study

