**Figure 2 Photos of SYMBOL CUP DM CEM and PE LINER medical devices.**

## **2.2. STATE OF KNOWLEDGE ON THE DEVICES UNDER EVALUATION**

SYMBOL CUP DMR HA and SYMBOL CUP DM CEM are class III implantable devices according to rule N°20 of the decree of April 20, 2006, laying down the rules for the classification of medical devices (transposition of Annex IX of directive 93/42/EEC and Directive 2005/50/EC).

These implants have been introduced on the market in France and elsewhere in Europe since the EC declaration of conformity of April 09, 2014ii. Conformity is based in particular on:

- Certificate N°27262 of device design examination according to Annex II section 4 of Directive 93/42/EEC issued by the Notified Body LNE/G-MED N°0459, updated by revision 5 dated September 01, 2015.iii
- The clinical evaluation « Cotyles de hanche, double mobilité, SYMBOL CUP DM » dated 28/11/2013 performed by Dedienne Santé, updated on 28/11/2014.iv
- And the validation of the clinical evaluation report by the Notified Body LNE/G-MED.v

The clinical evaluation of SYMBOL CUP DMR HA and SYMBOL CUP DM CEM as part of CE conformity is based on a literature review of equivalent products, with no data specific to these products. Nevertheless, the CE mark has authorized SYMBOL CUP DMR HA to be reimbursed by the French health insurance, under the Liste des Produits et Prestations Remboursables, under generic code 3168042 (reconstruction cup, modular, metal-back, without insert, uncemented) and SYMBOL CUP DM CEM under generic code 3150450 (standard cup, modular, metal-back, without insert, cemented). In both cases, the insert was covered under generic code 3161130 (solid polymer insert). The patients identified for this retrospective study benefited from reimbursement of the implant according to these generic codes.

Given the relatively recent market introduction of SYMBOL CUP DMR HA and SYMBOL CUP DM CEM, a patient cohort with a minimum 2-year follow-up, 2-year follow-up data and sufficient numbers was only reached in 2018. The retrospective study proposed here is therefore the first clinical evaluation specific to these products.

The number of units of SYMBOL CUP DMR HA and SYMBOL CUP DM CEM fitted in France are summarized in Table 3 and Table 4 respectively.

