### **3.2. PRIMARY ENDPOINT**

Implant survival rate at 2-year follow-up. This is the probability over time that the implant will remain in place in the living patient's hip. Events that reduce this probability are revision surgeries with removal of the implant, for whatever reason.

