## **10. STATISTICAL CONSIDERATIONS**

### **10.1. NUMBER OF SUBJECTS TO BE INCLUDED**

The size of the cohort considered to be the minimum in light of studies carried out by other manufacturers is at least 20 with a follow-up of 2 years.

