### **10.3. MAIN ANALYSIS**

Prothesis survival: Kaplan-Meier analysis.

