### **10.6. METHOD FOR TAKING INTO ACCOUNT MISSING, UNUSED OR INVALID DATA**

As the statistical analysis is descriptive, it will be carried out « *per protocol* » and missing data will not be substituted by values derived from hypotheses.

Visibly aberrant data that the investigator cannot obtain through the usual telephone follow-up will be excluded from the analysis.

Adverse event or follow-up dates for which the day is missing will be substituted by the mid-month date.

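### Does the 2-year follow-up entry rule let patients who died or were lost early drop out of the primary Kaplan-Meier analysis?

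*Combined protocol and SAP*

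**What the plan says.** The entry rule appears twice: "Patient having reach 2-year follow-up on March 01, 2018" in the section 1 summary, and "having reach 2-year follow-up on March 01, 2018" in section 7.1, where it is attached to any patient the surgeon operated on with either cup. No surgery-date window is given. Section 2.2 explains the timing by saying that "a patient cohort with a minimum 2-year follow-up, 2-year follow-up data and sufficient numbers was only reached in 2018", and section 10.1 sets the minimum cohort at "at least 20 with a follow-up of 2 years".

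The primary endpoint (section 3.2) is implant survival at 2 years: "Events that reduce this probability are revision surgeries with removal of the implant, for whatever reason". The whole of section 10.3 is "Prothesis survival: Kaplan-Meier analysis". Section 10.6, on missing data, begins "As the statistical analysis is descriptive, it will be carried out", continues with the label *per protocol*, and rules out imputation. It does not define an analysis set. Against bias, section 4.1 offers "Consecutive recruitment with provision of sampling frame data".

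**The concern.** Reaching 2-year follow-up can mean that two years have passed since surgery, or that two years of follow-up were actually observed. On the second meaning, with a per-protocol set on top, patients who died or were lost before two years would never enter the risk set. Kaplan-Meier exists to use such patients up to their last known date, and section 10.3 states no analysis set, time origin or censoring rule that would bring them back.

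The stakes are not trivial. Section 2.2 calls this the first clinical evaluation specific to these cups and says that the results will support CE-mark renewal and a reimbursement application. With a minimum of 20 patients, the placement of a single patient shows in the estimate.

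**Working it through.** **Step 1. Test both readings against the rest of the protocol.**

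| Place | Content | Fits elapsed time since surgery | Fits observed follow-up |
|---|---|---|---|
| 3.4, note | Patients without complaints usually have no 2-year visit | Yes | No: many well patients would be ineligible |
| 1, 5, 6.1; Annex 4 | Missing 2-year data are obtained by telephone once the study starts, which awaits the CNIL receipt (25 April 2018) | Yes | No: eligibility is fixed at 1 March 2018, before the calls |
| 4.1, 5 | Consecutive series, completeness checked | Yes | No |
| 6.1, 6.2 | Civil registry queried when a death is reported without a date | Yes | Hard to explain |
| 7.2 | Non-inclusion only for refusal, minority or guardianship | Yes | No: death and loss are not listed |
| Annex 2 | Death and dated revision fields in the 1-year and 2-year blocks | Yes | 1-year death field would be empty |
| 2.2, 10.1; Annex 5, Article 1 | Minimum 2-year follow-up | Yes | Yes |

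Only the last row suits observed follow-up, and it suits elapsed time equally well. Elapsed time implies surgery on or before 1 March 2016 (1 March 2018 less two years).

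**Step 2. What a standard analysis fills in.** Section 3.2 makes removal the only event, so death is not an event and is censored. The summary collects data to the latest news. Section 10.6 has a mid-month rule for incomplete follow-up dates, so such dates are expected. Annex 2 lists a date for the 1-year assessment and one for the 2-year telephone interview. Time from surgery, removal as event, and censoring at death or last news is the default.

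**Step 3. How much the literal reading would move the result.** Section 2.3 makes no assumption on event rates, so every rate and count below is an assumption. The minimum of 20 has no inputs and cannot be reproduced.

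*(a) Only unrevised patients are omitted.* Take n = 20 with one revision and c unrevised deaths or losses. Counting everyone gives S = 1 − 1/m, where m, the number at risk at the revision, lies between 20 − c and 20. Omitting them gives 1 − 1/(20 − c).

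| c | All counted | Omitted | Change (points) |
|---|---|---|---|
| 1 | 94.7–95.0% | 18/19 = 94.7% | 0 to −0.3 |
| 2 | 94.4–95.0% | 17/18 = 94.4% | 0 to −0.6 |
| 4 | 93.8–95.0% | 15/16 = 93.8% | 0 to −1.25 |

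With 24 patients, revisions at 3 and 8 months and three unrevised deaths or losses: 19/21 = 90.5% to 22/24 = 91.7% with all counted, against 19/21 = 90.5% with omission. The estimate stays the same or falls, so this does not flatter the device.

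*(b) A revised patient is also dead or lost before two years.* At n = 20, 19/20 = 95.0% (exact 95% CI 75.1–99.9%) becomes 19/19 = 100% (82.4–100%). In the 24-patient cohort, with one revised and two unrevised patients dead or lost, 20/22 = 90.9% to 22/24 = 91.7% becomes 20/21 = 95.2%, a rise of 3.6 to 4.3 points.

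*(c) On average.* With a share d of unrevised and r of revised patients dead or lost, the apparent survival is S(1 − d) / [S(1 − d) + (1 − S)(1 − r)]. For d = 0.10:

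| True S | r = 0.10 | r = 0.20 | r = 0.30 |
|---|---|---|---|
| 95% | 95.0% | 0.855/0.895 = 95.5% | 0.855/0.890 = 96.1% |
| 90% | 90.0% | 0.81/0.89 = 91.0% | 0.81/0.88 = 92.0% |

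Equal shares give no bias.

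*(d) The extreme reading.* If follow-up were taken to end at removal, every patient revised before two years would be dropped. Starting from 20 patients with the cup in place at two years, the result would be 100%. Counting everyone, with zero to four further deaths or losses, gives 95.2–96.0% with one revision and 87.0–88.9% with three: gaps of about 4 to 13 points. But survival would then be 100% by construction and the dated revision fields would serve no purpose. A living, traced patient who was revised qualifies under either reading of section 7.1.

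**The case for a change.** The best case for acting is that probable intent does not amount to a defined analysis set. Even if elapsed time is meant, an undefined per-protocol label could be used to drop patients without 2-year data. Annex 2 as published shows death and its reason without a separate date, and no field called date of last news. The minimum of 20 also depends on the reading: with 5%, 10% or 20% dead or lost before two years, 20/(1 − a) rounds up to 22, 23 or 25 implanted patients needed to have 20 with observed follow-up. A few sentences would settle all of this.

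Part of it stands. The surgery-date cut-off, the censoring rule and the unit (patient or hip) are not written down, and a good report will state them. But the per-protocol label sits in a sentence about not imputing values, in a non-comparative study with no assigned treatment and no required visits (sections 4 and 6.2). Its natural meaning there is eligible patients analysed as observed. The date of death is already to be obtained under section 6.1, and the assessment and interview dates can serve as last-news dates. The figure of 20 is a benchmark taken from other manufacturers' studies, not a power calculation, and nothing in the protocol follows from missing it.

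**Conclusion.** No change is needed. The wording is loose, but only the elapsed-time reading fits the telephone follow-up, the death tracing, the completeness check and the non-inclusion criteria. An ordinary Kaplan-Meier analysis then supplies the time origin and the censoring.

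No bias is shown. With unrevised deaths or losses only, the literal reading would move the estimate by 0 to 1.25 points at n = 20, downwards, against an exact interval at 19/20 that is 24.8 points wide (75.1–99.9%). A flattering shift of 3.6 to 5 points needs a patient who was both revised and then dead or lost. An average bias needs revised patients to be lost more often than others. The documents give no figure for either. The conclusion assumes that all eligible consecutive patients operated on by 1 March 2016 are counted, as the rest of the protocol implies.

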## **7.2. NON-INCLUSION CRITERIA**

Explicit refusal by the patient to allow data describing his pathology and treatment to be included in this study.

Minor patients or patients under guardianship.

### **7.3. RECRUITMENT PROCEDURES**

As this study is retrospective, patients were recruiting during routine care prior to the drafting of protocol.

## **8. RULES FOR STOPPING THE STUDY**

### **8.1. TERMINATION OF THE STUDY BY THE SPONSOR**

The sponsor may stop the study at any time, for the following reasons:

- Major protocol violations,
- In the event of a request to stop by authorities

### **8.2. TERMINATION OF THE STUDY BY THE INVESTIGATOR**

The investigator may stop participating in the study with agreement of the sponsor. The reason for the discontinuation of the study must be duly explained.

## **9. DATA COLLECTED**

The data is collected in the electronic patient record management system will be copied directly into a spreadsheet by the surgeon or on site by the CRA. 2-year follow-up data will be entered directly into the spreadsheet. The list of variables is in Annex 2.

## **10. STATISTICAL CONSIDERATIONS**

### **10.1. NUMBER OF SUBJECTS TO BE INCLUDED**

The size of the cohort considered to be the minimum in light of studies carried out by other manufacturers is at least 20 with a follow-up of 2 years.

### **10.2. DATA ANALYSIS – GENERAL INFORMATION: DESCRIPTIVE APPROACH**

- Descriptive statistics: preoperative, operative, postoperative
- Tabulation of adverse events
- Kaplan-Meier analysis of implant survival
- Comparison tests of preoperative versus 1-year and 2-year postoperative efficacy scores.

Tests will be performed with a two-side alpha risk of 5%. Confidence intervals will be at 95%.

Continuous variables will be tested using Student's t-test. Categorical variables will be tested using Chi-2 test.

No subgroup analysis is planned.

No interim analysis is justified given the strict retrospective nature of the study.

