### **3.4. SECONDARY ENDPOINTS**

- Safety: Intra and extra-prosthetic dislocation rates
- Safety: Incidence of other adverse events
- Effectiveness: Harris Hip Score (HHS)
- Effectiveness: Devane classification

Note: Since patients with no complaints requiring an orthopedic opinion do not usually present for a 2-year visit, only the functional questions of the 2-year HHS score will be collected during the telephone interview.

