### **10.4. SECONDARY ANALYSES**

Subgroup analyses: Not applicable

- Descriptive statistics
- Continuous variables: Student's t-test or non-parametric tests in case of a breach of the conditions for applying parametric tests.
- Categorial variables: Chi-2 test.

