**Annex 2: List of study variables**
**DATA FROM THE COHORT SYMBOL CUP DMR HA AND SYMBOL CUP DM CEM**

PREOPERATIVE DEMOGRAPHICS	Order number of the surgery with this type of implant
	Type of implant DMR HA or CEM
	Month/year of birth
	Sex
	Surgeon identification
	Date of preoperative visit
	Height (cm)
	Weight (Kg)
	BMI
	BMI class
	Operated side
	Etiology / diagnosis
	Medication
	Medication - Specify
	Medical history
	Medical history - Specify
	Local surgical history on the affected hip
	Local surgical history on the affected hip - Specify
	Surgeon's comments
PREOPERATIVE DEVANE & CHARNLEY CLASSIFICATIONS	DEVANE
	CHARNLEY
HHS PAIN	Pain
HHS FUNCTIONAL ABILITIES - WALKING	Lameness
	Support
	Walking perimeter
HHS FUNCTIONAL ABILITIES – DAILY LIFE	Socks and shoes
	Stairs
	Sitting position
	Public transport
HHS – MOBILITY	Flexion °
	Extension °
	Abduction °
	Adduction °
	External rotation °

	Internal rotation °
	TOTAL MOBILITY
DEFORMATIONS	LLI (cm)
	Flessum °
	Adductum °
	Internal rotation °
	TOTAL DEFORMATIONS
	TOTAL PREOPERATIVE HHS
SURGICAL INTERVENTION	Date of surgery
	Age at surgery
	Intervention duration (min)
	Surgical approach
	Type of intervention
	Surgeon's comments
	Operative adverse events
ACETABULAR COMPONENTS	Cup walls
	Fragile acetabulum zone
	Cup identification
	Size
	Cement
	Reaming diameter
	Liner
	Femoral head
	Diameter
	Bone graft
	Screw
	Pegs
	Associated surgical procedure
FEMORAL STEM	Stem identification
	Cement
	CCD angle
	Collar
	Broach size
	Stem size
	Neck length
	Bone graft
STABILITY	Stability of the hip
INCIDENTS	Operative adverse events
SURGEON'S COMMENTS – END OF SURGERY	Surgeon's comments
1-year postoperative assessment	Date
	Death

	Reason for death
1-year postoperative assessment	
DEVANE & CHARNLEY	DEVANE
CLASSIFICATIONS	CHARNLEY
HHS PAIN	Pain
HHS FUNCTIONAL ABILITIES - WALKING	Lameness
	Support
	Walking perimeter
HHS FUNCTIONAL ABILITIES – DAILY LIFE	Socks and shoes
	Stairs
	Sitting position
	Public transport
HHS – MOBILITY	Flexion °
	Extension °
	Abduction °
	Adduction °
	External rotation °
	Internal rotation °
	TOTAL MOBILITY
DEFORMATIONS	LLI (cm)
	Flessum °
	Adductum °
	Internal rotation °
	TOTAL DEFORMATIONS
	TOTAL 1-YEAR FU HHS
Adverse events and reason	Adverse events at 1-year FU
	Date of occurrence of the adverse event
	Potential reason
Treatment	Without revision surgery
	Surgical revision without component revision
	Surgical revision with revision of components
	Date of revision surgery
	Adverse event solved Yes/No

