	Unsolved adverse event – reason
Radiologic assessment at 1 year	Global offset
	Global length
	Cup
	Cup inclination
	Face stem

	Profile stem
	Surgeon's comments
2-year postoperative assessment	Date of telephone interview
	Death
	Reason for death
2-year postoperative assessment DEVANE & CHARNLEY CLASSIFICATIONS	DEVANE
	CHARNLEY
HHS PAIN	Pain
HHS FUNCTIONAL ABILITIES - WALKING	Lameness
	Support
	Walking perimeter
HHS FUNCTIONAL ABILITIES – DAILY LIFE	Socks and shoes
	Stairs
	Sitting position
	Public transport
HHS FUNCTIONAL ABILITIES TOTAL	HHS FUNCTIONAL ABILITIES TOTAL AT 2-YEAR FU
Adverse events and reason	Adverse events at 2-year FU
	Date of occurrence of the adverse event
	Potential reason
Treatment	Without revision surgery
	Surgical revision without component revision
	Surgical revision with revision of components
	Date of revision surgery
	Adverse event solved Yes/No
	Unsolved adverse event – reason

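### Chi-2 is the only test named for categorical variables, but the planned efficacy comparisons are before and after surgery in the same patients, so Devane would be tested as if the ratings were independent

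*Combined protocol and SAP*

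**What the plan says.** - **Test rule.** Section 10.2 says "Categorical variables will be tested using Chi-2 test". Section 10.4 says "Categorial variables: Chi-2 test". The only fallback, "non-parametric tests in case of a breach of the conditions for applying parametric tests", is in the line for continuous variables.
- **Planned efficacy tests.** Section 10.2 lists "Comparison tests of preoperative versus 1-year and 2-year postoperative efficacy scores", at two-sided 5%.
- **Design.** Section 4 describes the study as "Non-comparative", so a before/after contrast can only be within patients.
- **Endpoint.** Section 3.4 lists "Effectiveness: Devane classification". The section 1 summary also lists Charnley as an effectiveness endpoint; section 3.4 does not.
- **Data.** Annex 2 has "PREOPERATIVE DEVANE & CHARNLEY CLASSIFICATIONS", the same two items at 1 year, and "2-year postoperative assessment DEVANE & CHARNLEY CLASSIFICATIONS".
- **Size.** Section 10.1 sets a minimum of 20 patients, with no power calculation.

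Section 10 names no paired method for any variable. The documents do not say how many Devane classes there are or whether they are ordered.

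**The concern.** In its usual sense a Chi-2 test compares independent groups. Applied to Devane before and after surgery, it enters each patient twice, compares the class totals at the two times, and discards the information on who changed. The p-value then depends only on the totals.

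If a patient's two ratings are positively correlated, the variance that Chi-2 assumes for the difference is too large. The test rejects less often than 5% when nothing has changed, and a real change is more easily reported as not significant. With about 20 patients this can decide how an effectiveness endpoint is reported. Section 2.2 says the results will feed the CE-mark renewal and a reimbursement application.

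**Working it through.** The plan gives no figure to reproduce: the minimum of 20 is justified by other manufacturers' studies. The check therefore has three parts.

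**1. Worked example (20 pairs, two categories).** Favourable rating: 7/20 before, 13/20 after. Suppose 7 patients are favourable at both times, 6 gain, 0 lose and 7 are at neither.

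- Chi-2 as independent groups: pooled proportion 20/40 = 0.5, so Chi-2 = (13/20 − 7/20)² / (0.5 × 0.5 × 2/20) = 0.09/0.025 = 3.6, p = 0.058.
- Exact McNemar, 6 against 0: p = 2 × 0.5⁶ = 0.031.
- Mid-P McNemar: half of that here, 0.016, because no outcome is more extreme.
- Within-patient correlation (phi) in this table: (7×7 − 6×0)/√(7×13×13×7) = 49/91 = 0.54.

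The conclusion at 5% changes with the test. The same totals give Chi-2 p = 0.058 however the patients moved. If 13 had changed one way and 7 the other, exact McNemar would give 2 × P(Bin(20, 0.5) ≤ 7) = 0.26. That case requires every patient to switch category; it shows what Chi-2 cannot see and is not a realistic cohort.

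**2. Behaviour when nothing changes.** For two categories with proportion p at both times, the variance of the difference is 2p(1−p)(1−ρ)/n, but Chi-2 uses 2p(1−p)/n. The statistic is therefore about (1−ρ) times a chi-square on 1 df. At ρ = 0.5 the critical deviate becomes 1.96/√0.5 = 2.77, a two-sided rejection rate of about 0.6%. Simulation at n = 20 and p = 0.5 agrees (0.6%).

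For more classes the ratings were simulated from correlated normal scores: n = 20, 10,000 cohorts per setting, cut points −0.5, 0.5 (3 classes) or −1, −0.3, 0.3, 1 (5 classes). The number of classes, cut points and correlations are assumptions.

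| Latent correlation | −0.3 | 0 | 0.3 | 0.5 | 0.7 |
|---|---|---|---|---|---|
| Chi-2 rejection, 5 classes | 5.5% | 4.3% | 3.4% | 2.5% | 1.5% |
| Chi-2 rejection, 3 classes | 6.8% | 5.3% | 3.5% | 2.3% | 1.0% |

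Across separate runs the values at correlation 0.5 lay between 2.0 and 2.6%.

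**3. Power, with pairing and ordering kept apart.** At n = 20 and a shift of 0.8 SD, Chi-2 against Stuart-Maxwell (paired, ignores class order):

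| Latent correlation | 0 | 0.3 | 0.5 | 0.7 |
|---|---|---|---|---|
| 5 classes | 39 v 26% | 36 v 33% | 34 v 44% | 32 v 62% |
| 3 classes | 48 v 41% | 47 v 52% | 45 v 61% | 44 v 74% |

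Wilcoxon signed-rank, usable only if the classes are ordered, reaches 85% (5 classes) and 76% (3 classes) at correlation 0.5. Dichotomised, with the same shift and correlation: Chi-2 47%, exact McNemar 48%, mid-P McNemar 60%.

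**The case against.** **Devane may not be tested.** The planned tests concern scores, and Devane is called a classification. This stands: testing is implied, not stated. However, the before/after comparison is the only efficacy test planned, Devane is one of two effectiveness endpoints in section 3.4, and the categorical rule is repeated under secondary analyses.

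**Chi-2 may be meant for section 10.5, or may mean McNemar.** Comparing the cohort with the other patients in the sampling frame is a proper use. McNemar's statistic is also referred to a chi-square, and the t-test is not labelled as paired either. But sections 10.2 and 10.4 neither limit Chi-2 to 10.5 nor name a paired form. If a paired form was meant, the fix merely records it.

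**Pairing does not always gain power.** This stands. At low correlation with 5 classes Chi-2 has more power than Stuart-Maxwell, and the largest gaps come from using class order. At correlation 0.5, 5 classes and a shift of 0.5 SD, power is 11% (Chi-2), 15% (Stuart-Maxwell) and 48% (signed-rank), so only 4 of the 37 points come from pairing. The asymptotic Stuart-Maxwell test is itself conservative at n = 20 with 5 classes: 1.9% under no change at correlation 0.5, against 2.6% for Chi-2 in the same check. An exact or permutation version is therefore needed.

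**The study is descriptive.** Section 2.3 makes no hypothesis about endpoint changes. This limits the weight of the point but does not remove it, because section 10.2 still plans tests at 5%.

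**Conclusion.** The point holds as a conditional one: if Devane is tested before versus after surgery under the stated rule, the test does not match the paired data. The same applies to Charnley if the section 1 endpoint list governs. This is a stated rule that is wrong for that use, and not only missing detail.

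On size, at 20 pairs and an assumed latent correlation of 0.5, Chi-2 rejects about 2 to 2.6% of the time under no change, and the worked example moves from p = 0.031 to p = 0.058. The power gain from pairing alone depends on the assumed correlation and number of classes.

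A reader might infer three stronger things that the documents do not support:

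- That the plan definitely commits to a wrong Devane analysis. No section says that Devane will be tested.
- That efficacy could be falsely claimed. With positive correlation the error runs towards missing a change; only at negative correlation is Chi-2 slightly liberal.
- That the main result is at risk. The primary Kaplan-Meier analysis is unaffected, as only secondary analyses are involved.

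The wording should be corrected, as a point of secondary importance.

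**What to change.** First state whether Devane is tested, and reconcile sections 1 and 3.4 on Charnley. Then replace the categorical rule in 10.2 and 10.4 with wording such as:

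> Any preoperative versus 1-year or 2-year comparison of a categorical endpoint (Devane, and Charnley if retained) uses a paired test on complete pairs: Wilcoxon signed-rank if the classes are ordered; otherwise an exact or permutation test of marginal homogeneity; mid-P McNemar if dichotomised. The number of complete pairs and the before/after cross-table are reported at each time. Chi-2, or Fisher's exact test when expected counts are small, is used only to compare groups of patients, as in section 10.5. The t-test for the Harris Hip Score is paired.

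Mid-P is named because the exact McNemar test gains almost nothing over Chi-2 at n = 20 and correlation 0.5 (48% against 47%).

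The cost is a few lines of text. No extra data are needed, since Annex 2 already collects both classifications at all three times.
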